#### 10.1.7 Exploratory Analyses of Mechanistic and Inflammatory Biomarkers

Mechanistic and inflammatory endpoints will be studied to gain insight into the molecular mechanism of action of the dexamethasone treatments and to generate hypotheses for future

research. The mechanistic outcome measures may include, but will not be limited to, single-protein single-channel recordings, organellar and single-cell current (Ca+2, and pH), fluid secretion by acinar cells, and ductal secretory and signaling functions. These mechanistic endpoints will be summarized by study day and as change from baseline. Summary statistics employed may include means, geometric means, minimum and maximum values, standard deviations, 90% confidence limits, medians, and frequencies as appropriate for the measure. Log or other transformations may be used if they improve the distributional properties of the outcome measure.

Saliva-derived biomarkers of inflammation and salivary gland dysfunction may be identified from the exosomal microRNAs and non-coding small RNAs. The frequency of the presence/absence of these biomarkers in the saliva both before and after treatment will be reported. Concentrations of biomarkers above the threshold of detection will be summarized using the summary statistics listed above. Biomarkers for inflammation other than non-coding RNAs might be measured in saliva, but those biomarkers will be determined by findings in the biopsies.

Finally, mechanistic endpoints and biomarkers (including changes from baseline) that appear promising will be tested for association with inflammation, salivary flow, or other measures of salivary gland dysfunction. Cross-sectional analyses may include measures of correlation such as Kendall's tau, Spearman rank correlation, and polyserial correlation, as appropriate for the measure. Biomarkers or outcomes that show evidence of correlation with salivary flow or salivary gland dysfunction may be further analyzed longitudinally using mixed-models analysis. These analyses are considered exploratory and hypothesis generating and, as such, will not be corrected for multiple comparisons.

#### 10.1.8 Criteria for Significance

The hypothesis test and confidence interval of treatment effects for the primary analysis will be one-sided and test for a positive treatment effect. Hypothesis tests and confidence intervals of secondary analyses will be either 1- or 2-sided as described above. All statistical tests will use an  $\alpha = 0.05$ .

#### 10.1.9 Interim Analysis

No interim analysis will be performed.

## 10.2 **Power Analysis**

The primary endpoint is the change in salivary flow (Day 56 – Day 0) following either saline (placebo) or dexamethasone irrigation. Because each subject will simultaneously receive both irrigation treatments over several time points, the experimental design is a doubly-repeated-measures design with one repeated effect for treatment and another repeated effect for study day, and random effects for subject. The expected treatment effect of the dexamethasone irrigation over the saline (placebo) irrigation is an improvement in salivary flow of at least 40%.

The power and sample size computations assume the final primary analysis will be doublyrepeated-measures analysis, including an unstructured variance and random effects for subject to account for the non-independence between glands within a subject. The "unstructured variance" allows the variances (SDs) of the change in salivary flow for each treatment to differ from each other. The power analysis was performed in SAS using the methodology described by Kononoff and Hanford.

The power analysis is based upon the variance parameter estimates in Table 10-1.

Parameter	Estimate
1. Standard deviation of the change in salivary flow for the saline-irrigated parotid gland	0.0168
2. Standard deviation of the change in salivary flow for the dexamethasone- irrigated parotid gland	0.0906
3. Within subject correlation between parameters 1 and 2 above	0.15

The SDs of the change in salivary flow for the placebo and dexamethasone irrigations were estimated from data published by Izumi et al. the mean measures and SDs of change in total salivary flow during 2 minutes were converted to flow from a single parotid gland during 1 minute by multiplying by 0.1625 (0.65 for the proportion of total flow from the parotid glands x 0.5 for a single parotid gland x 0.5 for 1 minute). This conversion assumes a very high correlation between total salivary flow and parotid salivary flow.

The above power analysis at 80% power determined that 16 patients would be required to detect a one-sided 40% increase in dexamethasone-irrigated parotid glands compared with the saline-irrigated parotid glands with respect to change in salivary flow from Day 0.

Approximately 20 subjects will be screened to ensure that 16 subjects will be randomized and treated with dexamethasone irrigation. Subjects who discontinue from the study before the Stage I screening parotid irrigation will be replaced. Subjects who do not receive the first irrigation treatment and at least 1 post-treatment salivary flow assessment will also be replaced.

# 11 HUMAN SUBJECTS PROTECTION

### 11.1 Subject Selection

Selection of subjects will not be limited by race or ethnicity. Because SS occurs most frequently in adult females, males and children will be excluded from the study. This inclusion strategy is important in a small study like this to insure as homogeneous a population as possible to stabilize the variance. Also, recruitment may be difficult in males and children because it is uncommon. Having a very small set of males or children would make it difficult or even impossible to statistically adjust for their unique contribution to the data.

# 11.2 Justification for Exclusion of Children

Because SS occurs most frequently in adults, with less than 145 total cases of primary SS reported internationally, children will be excluded from the study to reduce variability of results.

### 11.3 Justification for Exclusion of Non-English speaking Subjects

Subjects that are not able to understand written English will not be included in the study. Subjects will be asked to complete several validated data questionnaires that are not translated and validated in their native languages.

### 11.4 Justification for Exclusion of Other Vulnerable Subjects

Pregnant women will be excluded from the study because dexamethasone should not be used during pregnancy because the potential benefit does not justify the potential fetal risks.

### 11.5 Justification of Sensitive Procedures

Although placebo will be used in the study, each subject will also receive active treatment. The placebo treatment will serve as a comparator in evaluating subject response to dexamethasone

CNS and NIDCR IRB Protocol Template (rev.9.21.11)Page 45 of 58

treatment. Withholding salivary stimulants will be necessary 24 hour prior to saliva collections to determine baseline salivary flow.

#### 11.6 Safeguards for Vulnerable Populations

All subjects of childbearing potential will be required to use an effective method of contraception during the study. A pregnancy test will also be performed before any procedures requiring radiation and prior to any study treatment. Women who are lactating will be excluded from the study because dexamethasone, which is secreted in breast milk, could suppress growth or endogenous corticosteroid production in the breastfed child, or cause other unwanted effects.

# 12 ANTICIPATED BENEFIT

Subjects participating in this study may benefit from improved salivary function, which is important in the daily activities of chewing, swallowing, and speaking and is vital to good dental and oral health.

# 13 CLASSIFICATION OF RISK

This study is classified as research involving more than minimal risk with the prospect of individual benefit. The risk is justified given the lack of effective treatments for many patients with xerostomia due to primary SS.

# 14 CONSENT DOCUMENTS AND PROCESS

### 14.1 **Designation of Those Obtaining Consent**

The study investigators designated as able to obtain consent in Table 11-1, will obtain informed consent.

### 14.2 **Consent Procedures**

Investigators qualified and designated in Table 11-1 of the protocol will obtain informed consent. Written, informed consent will be obtained before any screening or study procedures are initiated. All participants will receive a verbal explanation in terms suited to their comprehension of the purposes, procedures, and potential risks of the study and of their rights as research participants. Participants will have the opportunity to carefully review the written consent form and ask questions regarding this study prior to participation.

#### 14.3 **Consent Documents**

#### 14.3.1 Designation of Those Obtaining Consent

Study investigators designated as able to obtain consent above will obtain informed consent.

#### 14.3.2 Consent Procedures

For inclusion in the study, each subject will be required to sign the patient population consent form. Participants will have the opportunity to carefully review the written consent form and ask questions regarding this study prior to signing. The original consent forms will become part of the permanent medical record, and copies will be provided to the subjects. A copy of the consent form can be found in Section 25. The fact that informed consent was obtained prior to the initiation of study procedures will be documented in the subject's medical or research record.

#### 14.3.3 Consent Documentation

The consent form has all the required elements

# 15 DATA AND SAFETY MONITORING

#### 15.1 Data and Safety Monitor

The principal investigator will be responsible for monitoring the conduct of the study and verifying adherence to the protocol. The NIDCR Data and Safety Monitoring Committee (DSMC) will have safety oversight responsibilities for the study. The committee will include members with expertise in a broad range of areas, including human subjects' protection, research ethics, clinical trial implementation, biostatistics, and rheumatology.

### 15.2 Data and Safety Monitoring Plan

Approximately annually, the DSMC will review data related to enrollment progress, study implementation, subject safety, and protocol violations. The DSMC will also consider current information from other sources on the biology of the disease and the subject population under study. Based on these reviews, the DSMC will make recommendations to the principal investigator and the NIDCR Clinical Director concerning the continuation, modification, or termination of the study. The DSMC will also meet ad hoc if relevant issues arise that require committee review. The roles and responsibilities of committee members and meeting procedures will be formally described in a charter.

#### 15.3 Criteria for Stopping the Study or Suspending Enrollment or Procedures

The DSMC chair will be alerted if any of the following situations occur:

- An unexpected fatal or life-threatening event assessed as related to the use of study drug.
- Three or more subjects with similar severe AEs assessed as related to the use of study drug.
- Three or more subjects with SAEs assessed as related to the use of study drug.
- Any occurrence of facial nerve paralysis related to a study procedure.
- Three or more occurrences of bacterial parotid infection requiring antibiotic administration, assessed as related to a study procedure or study drug.

The principal investigator will be responsible for monitoring the accruing safety data related to suspension guidelines and for alerting the DSMC chair when a criterion is met. The DSMC chair will be alerted by email within 7 calendar days of determination that a criterion has been met. The DSMC will issue a recommendation on study continuation to the NIDCR Clinical Director after reviewing data related to the suspension guideline. If the study is stopped, subjects will receive conventional care for any study-related AEs and continue to be followed for clinical and safety outcomes. Otherwise, the study will continue per the DSMC recommendations. The principal investigator and the Clinical Director will provide the recommendations of the DSMC to the IRB.

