#### 4.4 **Study Procedures**

The study scheme depicted in Figure 4-1 presents the study schedule of events. All procedures described are for the purposes of participation in this study and considered research..

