# 7.3 Parotid Fill Volume Determination and Saline Irrigation of Parotid Gland

Parotid fill volume will be measured before irrigations. Each subject will undergo 3 irrigations of each parotid gland, the first of which will use saline only. This procedure will involve placement of a catheter within Stensen's duct and filling of the duct with the appropriate solution, either dexamethasone or normal saline. The procedure may cause minor trauma to the parotid ducts and/or infection or inflammation of the parotid gland (sialadenitis). Other rare risks include perforation and/or scarring of the parotid duct(s) and damage to the facial nerve secondary to inflammation, infection, or scarring.

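### The three general DSMC-chair triggers in Section 15.3 count only drug-related events, so most severe or serious harm from research procedures requires no prompt alert to the chair

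*Protocol*

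**What the plan says.** Protocol Section 15.3 names five situations that oblige the principal investigator to alert the DSMC chair, by email, within 7 calendar days of determining that a criterion is met:

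1. "An unexpected fatal or life-threatening event assessed as related to the use of study drug"
2. "Three or more subjects with similar severe AEs assessed as related to the use of study drug"
3. "Three or more subjects with SAEs assessed as related to the use of study drug"
4. "Any occurrence of facial nerve paralysis related to a study procedure"
5. "Three or more occurrences of bacterial parotid infection requiring antibiotic administration, assessed as related to a study procedure or study drug"

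The section heading covers suspension of procedures as well as of enrollment.

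Section 4.4 says of the visit procedures: "All procedures described are for the purposes of participation in this study and considered research". Section 7 attaches risks to them. For cannulation and irrigation, Section 7.3 states: "Other rare risks include perforation and/or scarring of the parotid duct(s) and damage to the facial nerve secondary to inflammation, infection, or scarring". Section 7.5 reports hematomas and one parotid fistula after core needle biopsy. Section 7.8 describes rare severe contrast reactions and, in renal failure, a gadolinium-related condition that has caused some deaths. For the drug itself, Section 7.4 expects very little systemic exposure.

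**The concern.** The list treats drug and procedure as different things. Bullet 4 names a procedure, and bullet 5 names either ("assessed as related to a study procedure or study drug"). Bullets 1 to 3 name the drug alone, so they cannot safely be read as covering procedures. Yet these three are the only bullets that catch harm of a kind not foreseen by name.

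At stake is the speed of independent oversight. If a research procedure caused a death or several serious injuries, the protocol would not oblige anyone to tell the DSMC chair promptly, and further subjects could undergo the same procedure before the committee's next scheduled look.

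**Working it through.** No figure in the protocol is in dispute, so the check is a reading of the text plus one small count.

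**Step 1. Classify the triggers by required attribution.** Drug only: bullets 1, 2 and 3. Procedure only: bullet 4. Either: bullet 5. That is 3 + 1 + 1 = 5. Both bullets that admit procedures are restricted to a single named event type.

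**Step 2. Ask which procedures can be separated from study drug.** By Section 4.3 and Table 4-1, the bilateral saline irrigation with fill-volume measurement falls in Screening Stage I. The first MRI, technetium scan and core biopsy fall in Stage II. Randomization and the first treatment irrigation are on Day 0. Harm from these screening procedures precedes any study drug. Section 10.1.1 starts the Safety Population at the screening saline irrigation, so these subjects already count for safety.

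**Step 3. Run example events through the five bullets as written.**

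| Event, attributed as shown | Bullet met |
|---|---|
| Death after contrast MRI, attributed to contrast | none |
| Life-threatening bleed after core biopsy, attributed to biopsy | none |
| Three subjects with SAEs from screening cannulation (not infection, not nerve paralysis) | none |
| One facial nerve paralysis from biopsy or cannulation | 4 |
| Three bacterial parotid infections needing antibiotics, from a procedure | 5 |
| Duct injury during a Day 0 or Day 28 irrigation | depends on whether the assessor calls it drug-related |

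**Step 4. Check whether another section supplies the missing alert.**
- Section 8: every SAE goes to the CROMS Product Safety group and is reviewed by its medical monitor. The DSMC is not named.
- Section 17: deaths go to the Clinical Director within 7 days; serious unanticipated problems go to the IRB and Clinical Director, also within 7 days. The DSMC is not named.
- Section 15.2: the DSMC reviews safety data about annually and may meet ad hoc when relevant issues arise. No event is defined that compels such a meeting.

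None of these requires prompt notice to the DSMC.

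**Step 5. Exposure between reviews.** Section 4.2 allows up to two years of recruitment. Section 10.2 plans about 20 screened and 16 treated. Assuming even enrollment over the full two years, 16 / 2 = 8 to 20 / 2 = 10 subjects enter per annual interval. Faster or clustered recruitment would raise this.

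**The case against.** The best defence is that the list is a deliberate design: general triggers for the drug, plus specific triggers for the two procedure harms the sponsor singled out, one of them at the first case. That stands to this extent: the differing phrases are not a contradiction, and the gap does not cover all serious procedure injury.

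Second, the events are not lost. The Clinical Director, who receives the DSMC's recommendations, hears of a death within 7 days, about as fast as the chair would be emailed. The DSMC may meet ad hoc under a charter that is not shown, and Section 15.3 does not forbid raising other events. This also stands. A reader might infer that procedure harm would go undetected; Sections 8 and 17 show otherwise. The remaining gap is one mandatory alert to the independent committee.

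Third, Section 4.4.12 uses the term study drug where it describes dispensing both dexamethasone and placebo, so harm during either randomized irrigation might be assessed as drug-related. This is fair, but it leaves the matter to the assessor and does not readily extend to screening cannulation, biopsy or contrast.

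Fourth, a reader might quantify the gap from the biopsy complication rate in Section 7.5, 5/319 = 1.57%. With 16 × 2 = 32 biopsies, 32 × 5/319 = 0.50 complications are expected, and P(at least one) = 1 − (1 − 5/319)^32 = 0.40. This does not measure the gap. The source rate is per patient; four of the five events were hematomas, most needing no intervention; and the fistula was in a patient with metastatic carcinoma. Even if every complication were an SAE in a different subject, P(three or more in 32) = 1 − 0.603 − 0.307 − 0.076 = 0.014. The number of biopsies is not fixed either, since the Day 56 biopsy can be omitted and screened-only subjects can add some. Counting the share of procedures that involve dexamethasone is no better, because it says nothing about the risk of each.

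Finally, Section 7.8 ties the gadolinium deaths to renal failure and omits contrast when filtration is below 60 mL/min or hypersensitivity is suspected. That lowers the risk but does not change what the triggers count.

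**Conclusion.** The point holds as a gap in oversight. As written, one death, or any number of severe or serious events, attributed solely to a research procedure meets no alert criterion unless it is facial nerve paralysis or the third antibiotic-treated bacterial parotid infection. The consequence is the loss of a mandatory 7-day alert to the DSMC, leaving annual or discretionary review.

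This rests on reading study drug in bullets 1 to 3 as excluding procedures, which the list's own wording supports, and on there being no further notification duty in the unseen DSMC charter. The documents give no basis for a probability that the gap would matter. In a single-site pilot with 16 treated subjects it is probably small. No endpoint, analysis or stated figure is affected. A reader might infer a fault that must be corrected before the trial proceeds; the other reporting routes and the two existing procedure triggers do not support that rating. It is a worthwhile, cheap improvement.

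**What to change.** In Section 15.3, bullets 1 to 3, change the relatedness condition to *related to study drug or a study procedure*, in line with bullet 5. Leave every threshold, and the restriction of bullet 1 to unexpected events, as they are.

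The cost is one phrase in three bullets and a slightly higher chance of an ad hoc DSMC alert. For SAEs, Section 17 already has the principal investigator judge relatedness to the research, so little is added there. For severe but non-serious events, relatedness to a procedure must also be recorded. Three duct injuries, for example, would trigger an alert under the new wording only if they were graded severe or were serious.

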#### 7.5 Ultrasound-guided Parotid Gland Core Needle Biopsy

Subjects will undergo a core needle biopsy of the right parotid gland during the Screening Period and on Day 56. Ultrasound guidance will be used to localize the biopsy site within the gland, and local anesthetic will be administered to minimize pain during the procedure.

Several recent publications have described ultrasound-guided core needle biopsy of the parotid gland as a low-risk alternative to open surgical biopsy. Available published data indicate that the procedure is relatively simple and safe to perform and yields sufficient tissue for accurate pathologic diagnosis. The diagnostic accuracy (mainly for tumors) in 319 patients was 96% to 100%, with only 5 (1.6%) reported complications. Four of these complications were hematomas, most of which did not require any intervention. One patient with metastatic squamous cell carcinoma developed a parotid fistula after biopsy. The main risk of an open biopsy of the parotid is injury to the facial nerve (controlling motor function on the ipsilateral face); however, no such complication has been reported with ultrasound-guided core needle biopsy of the parotid, no SAEs were reported. One subject had an infected hematoma that responded promptly to antibiotics. The most common complaint was mild to moderate pain or discomfort at the site of the biopsy, which responded to simple analgesics. Other possible risks with the core needle biopsy are allergic reactions to the local anesthetic, bleeding at the biopsy site, and local infection; however, such events are rare.

Subjects in this study will be screened for a history of bleeding disorder and have a CBC with differential and platelets, PT, and PTT before each core needle biopsy. Any discomfort, pain, or swelling at the biopsy site will be treated with acetaminophen or more potent analgesics as needed. If facial nerve injury should occur, the subject will be referred to an appropriate subspecialist for care to minimize the damage. Subjects will be asked to sign a separate surgical consent form prior to the biopsy procedure.

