### 8 SUBJECT SAFETY MONITORING

All subjects will be monitored from the time of informed consent. Study procedures will be performed and monitored by licensed/certified NIH personnel. At each study visit, subjects will be evaluated for AEs and will be followed until resolution or stabilization of any AEs. All AEs will be graded according to a descriptive severity scale based on the National Institute of Allergy and Infectious Diseases (NIAID), Division of Acquired Immunodeficiency Syndrome Table for Grading the Severity of Adverse Events. The scale has been slightly modified for this protocol (Appendix 24.4 ). Pregnancy will be monitored throughout the study and subjects study participation will be stopped in the event of pregnancy. Emergency unblinding of a subject's

parotid gland randomization assignment will be allowed if the information is needed to treat a serious adverse event.

Serious adverse events will be reported to CROMS Product Safety group; each event will be reviewed by a CROMS medical monitor. The site's medically responsible Investigator will determine follow-up actions based on event intensity and whether it was expected and at least possibly related to study drug.

Subjects will be informed that they may withdraw or be excluded from the study at any time. The following conditions will require the discontinuation of study drug:

- Pregnancy
- New onset of a condition that requires treatment with any prohibited agent (Sections 3.3 and 6.2).
- Inability of study personnel to cannulate one or both parotid glands.
- Noncompliance with study procedures.
- Adverse event that would substantially increase the risk of continued participation.
- Investigator discretion.
- Violation of eligibility criteria.

Subjects who stop study treatment after receiving 1 of the two doses will be asked to complete the Day 56 assessments and the Safety Follow-up, excluding core needle biopsy of the parotid. Subjects who qualify for the study and who, prior to the first dose of study medication, elect to not receive treatment, will have the following assessments:

- Evaluation of AEs.
- Vital sign measurements (pulse rate, systolic and diastolic blood pressure, respiratory rate, and temperature).
- Laboratory tests if clinically indicated.

No additional data will be collected from subjects who withdraw completely from the study.

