# 17 ADVERSE EVENT, PROTOCOL DEVIATIONS AND UNANTICIPATED PROBLEM REPORTING

The Principal Investigator is responsible for detecting, documenting, and reporting unanticipated problems, adverse events (AEs), including serious adverse events (SAEs), and deviations in accordance with NIH policy, IRB requirements, and federal regulations. Relatedness to the research of all serious adverse events will be determined by the PI in consultation with the CD.

Serious unanticipated problems and serious protocol deviations will be reported to the IRB and CD as soon as possible and in writing on the Problem Report Form not more than 7 days after the PI first learns of the event. Not serious unanticipated problems and not serious deviations will be reported to the IRB and CD as soon as possible and in writing on the Problem Report Form not more than 14 days after the PI first learns of the event.

Deaths will be reported to the Clinical Director within 7 days after the PI first learns of the event.

All adverse events, deviations, and unanticipated problems will be summarized and reported at the time of Continuing Review.

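### Section 15.3 gives its two single-event safety criteria the same 7-day email alert as its three-event criteria, and the protocol requires no pause in other subjects until the DSMC has recommended

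*Protocol*

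**What the plan says.** Section 15.3 is headed as criteria for stopping the study or suspending enrolment or procedures. It names five situations. Two need only one event: an unexpected fatal or life-threatening event assessed as related to study drug, and any facial nerve paralysis related to a study procedure. The other three need three subjects or three occurrences.

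The prescribed response is the same for all five. The principal investigator monitors for the criteria and raises the alert: "The DSMC chair will be alerted by email within 7 calendar days of determination that a criterion has been met". Then: "The DSMC will issue a recommendation on study continuation to the NIDCR Clinical Director after reviewing data related to the suspension guideline". Section 15.3 gives no time limit for that review.

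Other sections add safeguards:

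- **Section 8.** Serious adverse events go to the product safety group, and "each event will be reviewed by a CROMS medical monitor". The medically responsible investigator decides follow-up actions according to the event's intensity, expectedness and possible relation to study drug.
- **Section 17.** "Relatedness to the research of all serious adverse events will be determined by the PI in consultation with the CD". Serious unanticipated problems go to the IRB and the Clinical Director as soon as possible, and "in writing on the Problem Report Form not more than 7 days after the PI first learns of the event".
- **Section 15.2.** The DSMC can meet ad hoc, and "The roles and responsibilities of committee members and meeting procedures will be formally described in a charter". The charter is not among the documents.

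On the risk itself, section 7.3 says of irrigation: "Other rare risks include perforation and/or scarring of the parotid duct(s) and damage to the facial nerve secondary to inflammation, infection, or scarring". Section 7.5 reports no facial nerve injury with ultrasound-guided core biopsy of the parotid and adds: "If facial nerve injury should occur, the subject will be referred to an appropriate subspecialist for care to minimize the damage".

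**The concern.** A criterion that is met by one event says that one such event is enough to question whether the trial should go on. Here it gets the same clock as a third antibiotic-treated parotid infection. The clock starts when the criterion is determined to be met, so the time from the event itself can be longer.

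If section 15.3 is followed to the letter, another subject could be irrigated or biopsied after a drug-related death or a procedure-related facial palsy and before the DSMC has been told, or while it is still reviewing. The irrigations and parotid biopsies are research procedures (section 4.4), so postponing one for a few days is clinically easy. Under section 15.3 the person who must raise the alert is the principal investigator, who also runs the trial and, with the Clinical Director, judges whether serious events are related. A stopping section is most useful when the first protective step does not rest on that person's discretion.

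**Working it through.** The 7 days is a stated rule, so there is no computed figure of the plan to reproduce. The check has three parts: whether a hold is required anywhere, how many procedures could fall in the interval, and what a hold would cost.

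**1. Is a hold required anywhere?**

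| Place | What it requires | Hold on other subjects? |
|---|---|---|
| 15.3 | Alert within 7 calendar days of determination, then DSMC review | None stated before the recommendation |
| 15.2 | Approximately annual and ad hoc DSMC meetings; charter | None stated; charter not shown |
| 8 | SAE reporting, medical-monitor review, investigator's follow-up actions; discontinuation rules | Not expressly; the discontinuation rules concern the affected subject |
| 17 | Relatedness of SAEs judged with the Clinical Director; reports to IRB and Clinical Director | None stated |
| 7.5 | Referral of an injured subject | None stated |

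**2. Procedures falling due in 7 days**

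Inputs: 16 subjects treated and up to 20 enrolled (section 3.1); one screening irrigation and two randomised sessions each (sections 4.4.6, 4.4.12 and 7.3); core biopsy at Stage II and Day 56 (section 4.4.9); recruitment of up to two years (section 4.2).

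Assumption: an even spread over 104 weeks (recruitment only) to 126 weeks (104 + 12 for screening + 8 to Day 56 + 2 for the late visit window).

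Formula: expected procedures in 7 days = number of procedures / number of weeks.

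- Irrigation sessions: 16 × 3 = 48, up to 20 + 32 = 52.
- Core biopsies: 16 × 2 = 32, up to 20 + 16 = 36.
- Total: 80 to 88.

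| Case | Low | High |
|---|---|---|
| Facial paralysis, all subjects | 80/126 = 0.63 | 88/104 = 0.85 |
| Facial paralysis, without the affected subject | (45 + 30)/126 = 0.60 | (49 + 34)/104 = 0.80 |
| Drug event, randomised sessions only | 32/126 = 0.25 | 32/104 = 0.31 |
| Drug event, without the affected subject | 30/126 = 0.24 | 30/104 = 0.29 |

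With a Poisson count, the chance of at least one procedure in another subject within 7 days is 1 − exp(−m). For facial paralysis that is 1 − exp(−0.595) = 45% to 1 − exp(−0.798) = 55%. For a drug event it is 1 − exp(−0.238) = 21% to 1 − exp(−0.288) = 25%.

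Sensitivity of the all-subject figure for facial paralysis:

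- If every Day 56 biopsy is dropped, as section 4.4.9 permits when baseline is uninformative: (48 + 16)/126 = 0.51 to (52 + 20)/104 = 0.69.
- If recruitment took one year (52 to 74 weeks), an assumption the protocol does not make: 80/74 = 1.08 to 88/52 = 1.69.

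Time taken by the DSMC review adds to these figures. The protocol gives no length for it.

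**3. What a pause would cost**

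- *Day 28 irrigations.* 16/126 = 0.13 to 16/104 = 0.15 fall due per paused week, or 0.51 to 0.62 in four weeks. Table 4-1 allows ±5 days, so a delay of up to 5 days from Day 28 stays in window.
- *Power.* A subject who misses the Day 28 irrigation leaves the Primary Efficacy Population (section 10.1.2). She is not replaced under section 10.2 if she has a post-treatment flow value. Take the stated 80% at n = 16 as given and approximate the analysis by a paired t-test at one-sided 0.05. The implied standardised effect is 0.652. At n = 15 the noncentrality is 0.652 × √15 = 2.52 on 14 degrees of freedom, and power is 77.5%.
- *Stage II window.* Stage II falls within 6 weeks before Day 0, and the baseline biopsy at least 14 days before it (Table 4-1 and its footnote 6). Slack for a biopsied subject: 42 − 14 = 28 days, so at most about 4 weeks.
- *Day 56 biopsy.* The visit window is −3/+14 days. A longer biopsy hold could lose a focus-score value, a secondary endpoint (section 9.2).

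**The case against.** The best defence is that section 15.3 is a workable rule: named triggers, a responsible person, a deadline, a review body and a recipient for its recommendation. It calls its triggers suspension guidelines, which suggests a judged decision rather than an automatic halt. Preferring a mandatory hold to prompt expert review is partly a matter of taste. This stands in so far as nothing here is miscalculated or self-contradictory.

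A reader might infer that nobody with oversight would know for a week. The protocol does not support that. For a related fatal or life-threatening event, the Clinical Director takes part in the relatedness decision under section 17, and is also the official who receives the DSMC's recommendation. The medical monitor reviews each serious event, the investigator must decide follow-up actions without waiting for the DSMC, and 7 days is a maximum. A reader might also infer that treatment must go on meanwhile, or that the DSMC has no review deadline at all. Neither follows: no section forbids a voluntary pause, and the unseen charter may set a deadline.

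The triggers are also rare. The protocol describes the dose as small and topical, and reports no facial nerve injury with this biopsy technique. A pause has costs beyond Day 28 irrigations, namely the Stage II and Day 56 windows. These limit how long a pause can be without loss. They do not argue against having one.

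What survives is narrower: every safeguard listed is a reporting duty, a review or a discretion, and none requires other subjects to wait.

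**Conclusion.** The point holds as a cheap improvement to patient safety, of minor to moderate severity. For one drug-related death or life-threatening event, or one procedure-related facial paralysis, section 15.3 sets the same alert period as for the three-event criteria, and the protocol leaves any hold in other subjects to discretion.

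Exposure in the 7 days is less than one procedure in another subject: 0.60 to 0.80 after facial paralysis and 0.24 to 0.29 after a drug event. These figures rest on even accrual over 104 to 126 weeks and apply only if a trigger occurs. The documents give no probability for either trigger, so no unconditional risk can be stated. The conclusion is about what the protocol requires. It does not say that the investigators would in fact carry on, or that oversight is missing.

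**What to change.** Add to section 15.3, for the two single-event criteria only:

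- Once the event is assessed as at least possibly related to study drug or a study procedure, alert the DSMC chair promptly, for example within 24 hours of that assessment. The 24 hours is a suggestion, not a figure from the protocol. Counting from the assessment keeps the clock from starting before relatedness has been considered.
- From the same moment, pause new randomisation and the implicated procedure until the DSMC has issued its recommendation: randomised irrigation for a drug event, irrigation and/or core biopsy for facial nerve paralysis.
- Salivary flow collection and adverse event visits continue.
- Ask for an expedited DSMC review.

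The three-event criteria keep the 7-day alert.

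The change costs one or two sentences and nothing in alpha. If a trigger occurs, a short pause puts few Day 28 irrigations at risk, and losing one subject from the primary analysis costs about 2.5 percentage points of power. A randomisation pause beyond about 4 weeks could make a biopsied subject's Stage II assessments lapse. The waiver of repeat imaging and biopsy in section 4.3 covers only subjects already treated on Day 0 who then took an excluded medication. A biopsy hold beyond the Day 56 window could lose a focus-score value. Both are reasons for a quick review.
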